8.2 Blinding

The Dental Examiner(s) completing the dental examinations will be blinded to the subject sequence of treatments assigned. The subject, sponsor, and all other study staff will not be blinded to the treatment sequenced assigned.

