5.5 Non-Investigational Material

Material ID	Description	Source
Sensodyne ProNamel Fresh Breath Toothpaste	Treatment A toothpaste	Commercially available
3M ESPE Clinpro	Treatment B toothpaste	Commercially available
Colgate Cavity Protection Toothpaste	Treatment C toothpaste	Commercially available
Toothbrush	Soft toothbrushes dispensed to each subject for each period to ensure no cross contamination	3M
Gloves	Latex-free gloves for study dental examiner to complete dental exams	3M [REDACTED]
Disposable mirrors	For dental exams	3M
Gauze	For dental exams	3M
Suction tips	For dental exams	3M
Air water syringes	For dental exams	3M
Camera	Digital camera used to capture photos of the subjects' mouths at baseline and end of study visits	3M [REDACTED]
Paper towels	For clean up	3M [REDACTED]
Paper bags	For subjects to hold their toothpaste, 3M Oral Rinse, and toothbrush	3M [REDACTED]
Garbage can	With liner to dispose of any used dental materials	3M [REDACTED]
Clip boards	For study staff to use to record study information	3M [REDACTED]
Pens	For subjects to record questionnaire responses	3M [REDACTED]
Case Report Forms	Study evaluation forms	3M

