6.3 Test Procedures

6.3.1 Visit 1: Period 1 Baseline (Day 0)

- Subjects will report to the [REDACTED] facility for study baseline procedures
- Study Coordinator will complete the consenting process

[figure not shown]
- Study Coordinator and Dental Examiner will review inclusion and exclusion criteria
- The Dental Examiner will complete a dental examination
- Study Coordinator will randomize the subject to their treatment group and dispense the assigned toothpaste, 3M Oral Rinse, and subject diary
- Study Coordinator will collect demographic information
- Study Coordinator will provide verbal and written product use and subject diary instructions
- Subjects will initiate their treatment in the evening of baseline visit
- Study Coordinator will provide subject payment for the visit(s) and all follow-up visits at the Study Coordinator's discretion
- Study Coordinator will schedule follow-up visit(s)

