6.3.3 Visit 3: Period 1 End of Treatment (Day 21)

- Subjects will report to the [REDACTED] facility for study procedures
- Subjects will return completed subject diaries, study toothpaste tubes, and 3M Oral Rinse bottles.
- Dental Examiner will complete a dental examination, review subject diary, and record any AEs, as required
- Dental photographs may be taken by study staff if oral tissue sloughing or irritation are found at the dental exam of the affected areas
- Subjects will complete the questionnaire
- Study Coordinator will dispense the assigned toothpaste for at least a 1-week washout
- Study Coordinator will schedule follow-up visit(s)

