6.3.5 Visit 5: Period 2 Mid-Treatment (Day 38+)

- Subjects will report to the [REDACTED] for study procedures
- Dental Examiner will complete a dental examination, review subject diary and record any AEs, as required
- Dental photographs may be taken by study staff if oral tissue sloughing or irritation are found at the dental exam of the affected areas
- Study Coordinator will schedule follow-up visit(s)

6.3.6 Visit 6: Period 2 End of Treatment / End of Study (Day 49+)

- Subjects will report to the [REDACTED] for study procedures
- Subjects will return completed subject diaries, study toothpaste tubes and 3M Oral Rinse bottles.
- Dental Examiner will complete a dental examination, review subject diary and record any AEs, as required
- Dental photographs may be taken by study staff if oral tissue sloughing or irritation are found at the dental exam of the affected areas
- Subjects will complete the questionnaire

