8.0 Randomization

8.1 Randomization

Subjects will be numbered from 01 through 72. This number will be used to identify the subject on the case report forms. Subjects will be randomized in a 1:1:1 ratio into three different two-treatment sequences: (1) A-> C (2) B->C and (3) C->B. All seventy-two (72) subjects will be exposed to the high SLS toothpaste (C), 48 subjects will be exposed to the medium SLS toothpaste (B), and 24 subjects will be exposed to the no SLS toothpaste (A). See Appendix II for the randomization schedule.

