APPENDIX II – Randomization Schedule

Subject Number	Period 1	Period 2
01	B	C
02	A	C
03	C	B
04	B	C
05	C	B
06	A	C
07	C	B
08	A	C
09	B	C
10	B	C
11	A	C
12	C	B
13	C	B
14	A	C
15	C	B
16	B	C
17	A	C
18	B	C
19	A	C
20	A	C
21	B	C
22	C	B
23	B	C
24	C	B
25	A	C
26	C	B
27	A	C
28	C	B
29	B	C
30	B	C
31	A	C
32	C	B
33	B	C
34	B	C
35	A	C
36	C	B
37	A	C
38	A	C
39	B	C
40	C	B
41	C	B
42	B	C

Subject Number	Period 1	Period 2
43	B	C
44	A	C
45	B	C
46	A	C
47	C	B
48	C	B
49	C	B
50	A	C
51	B	C
52	B	C
53	A	C
54	C	B
55	B	C
56	C	B
57	A	C
58	B	C
59	A	C
60	C	B
61	C	B
62	A	C
63	B	C
64	B	C
65	C	B
66	A	C
67	A	C
68	B	C
69	C	B
70	C	B
71	B	C
72	A	C

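### Commit to a crossover logistic model for the blinded examiner findings, and make examiner diary review the same in both periods

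*Combined protocol and SAP*

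**What the plan says.** Section 8.2 states that "The Dental Examiner(s) completing the dental examinations will be blinded to the subject sequence of treatments assigned". It then says that "The subject, sponsor, and all other study staff will not be blinded to the treatment sequenced assigned".

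**Analysis.** Section 9.4.1 counts a subject as having sloughing if it is seen at an examination or reported by the subject during the three weeks. This composite has a committed mixed logistic model: subject as a random effect, with fixed effects for treatment, period, sequence and, unless dropped, treatment-by-period. Section 9.4.2, outcome (a), isolates the examiner's part: any non-zero index score among the 12 areas. It will be summarized by treatment group. It will be modelled only if that is judged appropriate, by a generalized linear model of which Poisson is the example. Treatment, period and sequence effects are named; a subject effect is not.

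**Diary review by the examiner.** Section 1.0 lists it at T=3 and T=6 only. Section 6.3 lists it at Visit 3 (6.3.3), Visit 5 (6.3.5) and Visit 6 (6.3.6), but not at Visit 2 (6.3.2).

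**The concern.** Self-report is a stated objective, so the composite is legitimate. If it turns out positive, though, the natural question is whether the blinded component points the same way. The plan promises rates for that component but no firm analysis. The one model family it names is a poor match for a binary outcome observed in two periods on the same person, and it could easily miss a real difference.

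The diary point concerns equal ascertainment. Toothpaste A is used only in Period 1, and C is used in Period 2 by 48 of its 72 users. An extra review confined to Period 2 would fall unevenly across the three toothpastes, in the same order as the SLS level in the 9.1 hypothesis.

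**Working it through.** The plan gives no power or precision for the examiner-only analysis. The power figures in 9.2 do reproduce (74.2% and 77.6% against 74% and 77%, from Fisher's exact test with 0.025 in each tail), but they treat the groups as independent and do not bear on this analysis.

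**1. What the model without a subject effect uses.** Three sequences by two periods give 6 cells. Intercept, treatment (2), period (1) and sequence (2) make 6 parameters. The C-B contrast is therefore the average of the within-sequence contrasts in sequences 2 and 3, with 24 subjects per cell.

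**2. Standard error under no C-B difference.** Assumptions, not in the documents: one yes/no result per subject and period, rate p of 20% or 30%, within-subject correlation r = 0.3.
- Variance of the log ratio that the Poisson model assumes: 1/(24p).
- Actual variance: (1 - p)(1 - r)/(24p). The factor (1 - p) arises because the outcome is yes/no; (1 - r) arises from the pairing.
- p = 0.2: ratio 0.8 x 0.7 = 0.56; model SE 0.456, actual 0.342, too large by a factor of 1.34.
- p = 0.3: ratio 0.7 x 0.7 = 0.49; model SE 0.373, actual 0.261, too large by a factor of 1.43.
- Rejection rate at a nominal 5%: 2Φ(-1.96 x 1.34) = 0.9% and 2Φ(-1.96 x 1.43) = 0.5%.

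**3. A true 15-point C-B difference.** Poisson model SE = ½√[2/(24pB) + 2/(24pC)]. Actual SE = ½√{2[a + b - 2r√(ab)]}, with a = (1 - pB)/(24pB) and b = (1 - pC)/(24pC).
- 20% against 35%: log ratio 0.560, model SE 0.405, actual SE 0.297. Power Φ[(0.560 - 1.96 x 0.405)/0.297] = 22%.
- 30% against 45%: log ratio 0.405, model SE 0.340, actual SE 0.230. Power Φ[(0.405 - 1.96 x 0.340)/0.230] = 13%.
- Paired analysis of the risk difference, SE = √{[pBqB + pCqC - 2r√(pBqBpCqC)]/48}, with q = 1 - p: 0.0754 and 0.0817. Power Φ(0.15/0.0754 - 1.96) = 51% and Φ(0.15/0.0817 - 1.96) = 45%.

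**4. Simulation of the same setting.**

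| | No difference | 15-point difference |
|---|---|---|
| Poisson, no subject effect | 0-0.4% | 12-20% |
| Logistic, respecting the pairing | about 5% | 42-45% |

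A rerun with 200,000 trials per setting, generating the pairs directly and using a logistic contrast with a pair-based variance, gave 0.5% and 12-19% for the first row and 4-5% and 46-50% for the second. The exact values depend on the paired method; the gap does not.

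**5. Diary reviews per treatment period.**

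| | A | B | C |
|---|---|---|---|
| Periods (Period 1 + Period 2) | 24 + 0 | 24 + 24 | 24 + 48 |
| Section 1.0: one review in each period | 1.0 | 1.0 | 1.0 |
| Section 6.3: one in Period 1, two in Period 2 | 24/24 = 1.0 | (24 + 48)/48 = 1.5 | (24 + 96)/72 = 1.67 |

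The period term in the 9.4.1 model removes a review effect that is constant on its scale; it is estimable because B and C each occur in both periods. The Cochran-Armitage test (9.4.2), the Fisher's tests in 9.4.3 and the 9.4.1 Fisher fallback on all data have no period term. The fallback on Period 1 data alone is unaffected.

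**The case against.** The best defence is that little is missing. The plan discloses that subjects are unblinded and makes self-report an objective. It already summarizes examiner-only incidence by treatment, and it names period and sequence effects for the secondary model. Poisson is only an example, and a statistician could add a subject effect or a robust variance when the time comes. Both periods end with a diary review, and adverse events are also assessed at Visits 2 and 5, so the extra review may change little. All of this stands. It makes the point a cheap improvement and not an error in the primary analysis, but it does not supply a commitment or settle the Visit 5 wording.

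Three stronger readings are tempting and not supported.

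- **That the examiner's blind is unprotected.** A reader might infer this because the sequence list is printed in Appendix II against the subject number (8.1: "This number will be used to identify the subject on the case report forms"), because commercial tubes come back at examination visits (6.3.3: "Subjects will return completed subject diaries, study toothpaste tubes, and 3M Oral Rinse bottles"), and because unblinded coordinators may scribe. Nothing says that the examiner holds the list or handles the tubes. Section 12.0 returns materials to the Investigator, 6.3.1 lists randomization after eligibility review and the examination, and the SOPs, the Monitoring Plan and some removed text are unseen. This is missing detail, not a demonstrated weakness.
- **That the 6.2 schedule contradicts 6.3.5.** The schedule has a row for diary collection and none for review. A diary can be reviewed at Visit 5 and collected at Visit 6.
- **That over-reporting on C makes a false positive likely.** The documents give neither the size nor the direction of any reporting bias. A figure would depend on assuming the bias falls on C alone, and the changes proposed here would not alter it.

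**Conclusion.** Two modest points hold.

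First, the blinded component of the primary endpoint has no committed analysis that uses the pairing, and the example model would lose more than half of the available power for C against B: about 12-20% against 42-45% for a 15-point difference. This rests on the assumed base rate and correlation, and on the Poisson example being used as written, with model-based standard errors and no subject effect. The error runs towards missing a difference, so it should not be read as a source of false positives.

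Second, Section 1.0 and 6.3.5 disagree on the Visit 5 diary review. If 6.3 is followed, review frequency rises with SLS level. That is unequal ascertainment by design, only partly handled by the period term; it is not evidence that results would be biased.

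**What to change.** **Analysis.** Keep the composite primary endpoint. In 9.4.2, commit to a logistic model with a random subject effect and fixed treatment, period and sequence effects for examiner-observed sloughing, labelled supportive, and state that a period counts as positive if either on-treatment examination does. The treatment-by-period term is left out because the other fixed effects already use all six cell means. Tabulate observed and self-reported incidence separately by treatment. Do not make agreement between the two a second significance hurdle. Do not read an effect seen only in self-reports as proof of bias: two examinations sample only about two days of each 21-day period.

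**Diary.** Reconcile Section 1.0 (T=2 and T=5) with 6.3.2 and 6.3.5 so that examiner review is the same in both periods. State that the 12-area score is completed before the diary is opened. The visit descriptions already list the steps in that order; the change makes it a rule.

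**Cost.** One more model on data already collected, and a fixed order of visit steps. The model may fail to converge if few events are seen at examinations, in which case the separate table stands alone. The primary test loses no power.

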4.0 Subjects

4.1 Subject Selection

Subjects may only participate if they meet all study-specific selection criteria and sign a study-specific informed consent form. Exclusion criteria numbers 21 through 27 must be confirmed by the Screening Dental Exam by the Dental Examiner.

4.2 Inclusion Criteria:

1. Able to understand and willing to sign the informed consent;
2. Willing to agree to maintain confidentiality of the study and study materials;
3. 3M employee aged 18 years and older;
4. Willing to return to the study facility for scheduled study visits and recalls;
5. Agree not to use other oral hygiene products (non-study toothpaste, non-study toothbrush, mouth rinse, chewing gum);
6. Agree to the study instruction and schedule.

4.3 Exclusion Criteria:

[figure not shown]
7. A member of the ██████████ staff or █████ product team for the device under investigation;
8. Have a dental appointment scheduled during study duration for professional cleaning;
9. Is pregnant, nursing, or planning to become pregnant within the study duration;

██████████

10. History of antibiotic therapy within the previous 30 days or have a condition that is likely to need antibiotic treatment over the course of the study (e.g., cardiac conditions requiring antibiotic prophylaxis such as heart murmurs, pacemakers, or prosthetic heart valves and prosthetic implants);
11. History of using a prescription antimicrobial mouth rinse during the past 3 months;
12. Currently taking medications which may alter gingival appearance/bleeding;
13. Currently using anticonvulsants, calcium channel blockers, or other medications with side effects known to impact oral health;
14. Participation in any other clinical study within the last 30 days;
15. Resides in the same household with a subject already enrolled in the study;
16. Known history of sensitivity to oral hygiene products;
17. Currently using tobacco products (cigarettes, chewing tobacco) or vaping products (e-cigarettes);
18. History of diabetes;
19. Have removable partial/full dentures;
20. Have orthodontic appliances;
21. Have medical or oral conditions that may compromise the subject's safety or interfere with the conduct and outcome of the study;
22. Have known sloughing within the last 3 weeks;
23. Have dry mouth;
24. Have widespread caries or chronic neglect;
25. Have gross pathological changes of oral soft tissues;
26. Have advanced periodontal disease (purulent exudate, tooth mobility, and/or extensive alveolar bone loss);

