4.4 Subject Recruitment, Screening, Consent

The [REDACTED] staff will recruit subjects using a confidential database [REDACTED] containing names of [REDACTED] to be listed in the database. Potential subjects will be contacted once via e-mail to explain the purpose of the study, study requirements, including inclusion/exclusion criteria, restrictions on activities, information regarding who to contact for more information and the dates the study will run. The e-mail will include a copy

of the informed consent form for the subjects to review. See Appendix I for example recruitment letter. If the subject agrees to participate, an appointment is scheduled. If any additional measures, such as advertising, become necessary, they will be submitted to the IRB prior to their initial use.

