5.0 Study Materials

5.1 Description

- 3M Oral Rinse: The principle components of the 3M Oral Rinse being used in this study are described in Section 1.0 of this document and are the same for all treatment arms being used in this study. 15mL of 3M Oral Rinse will be swished for about 30 seconds twice a day (morning and evening), after brushing teeth with assigned toothpaste, for each 3-week treatment arm.

- Treatment A consists of a no SLS containing toothpaste. For the study, subjects randomized to Treatment A will receive 1 tube of Sensodyne ProNamel Fresh Breath toothpaste. The information on the components of Sensodyne toothpaste are listed on the packaging and safety data sheet.
- Treatment B consists of a medium SLS containing toothpaste. For the study, subjects randomized to Treatment B will receive 1 tube of 3M ESPE Clinpro Tooth Creme toothpaste. The information on the components of 3M Clinpro toothpaste are listed on the packaging and safety data sheet.
- Treatment C consists of a high SLS containing toothpaste. For the study, subjects randomized to Treatment C will receive 1 tube of Colgate Cavity Protection toothpaste. The information on the components of Colgate toothpaste are listed on the packaging and safety data sheet.

Subjects will be randomized to take two treatment products in sequence: either A followed by C, B followed by C, or C followed by B. Each of the treatments will be used in combination with the 3M Oral Rinse.

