9.4.1 Primary Analyses

The primary endpoint is the incidence rate of sloughing. All sloughing clinically observed or subject-reported over the three-week treatment period will be recorded as an adverse event and coded using the MedDRA dictionary (with a preferred term of oral mucosal exfoliation). Differences in incidence rates will be tested for significance using a generalized logistic regression model that takes into account the crossover design with subject as a random effect and treatment, period, sequence and treatment-by-period interaction as fixed effects, non-significant treatment-by-period interaction effect will be dropped from the final model. In the event of failing convergence of the model or finding a significant treatment-by-period interaction (carry-over effect), the Fisher's Exact test maybe used to test for significant differences in sloughing rates among the treatment arms using all data or Period I data only, respectively.

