9.4.2 Secondary Analyses

The 95% confidence intervals will be computed for the sloughing rates for each treatment group using the Wilson score method. Significant trends in incidence rates across the treatment groups (from high to medium to no SLS toothpaste) will be tested using the Cochran Armitage test.

The oral mucosal sloughing index score will be used to compute the following two outcomes: (a) Overall subject-level incidence based on any non-zero score among the 12 oral areas examined, and (b) an average subject-level score based on the mean of 12 severity scores over all oral areas for each subject. These outcome scores will be summarized for each treatment group and if appropriate, will be analyzed using a generalized linear regression model such as a Poisson model to test for significant treatment, period and sequence effects.

The diary data will be used to compute treatment compliance with expected number of doses, and this will be summarized per period and treatment group.

Exploratory analysis may occur to examine the onset time and duration of adverse events.

The data collected on the subject acceptance questionnaire will be summarized by treatment group. If appropriate, these data will be analyzed for treatment differences using a generalized linear regression model such as an ordinal logistical model that takes into account the cross over design and the ordinal nature of the data.

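### Subjects know which branded toothpaste they are using, although their report alone can make a primary sloughing event and acceptability is wholly self-reported

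*Combined protocol and SAP*

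**What the plan says.** Section 3.1 calls the study single-blind, and Section 8.2 says who is blinded. The examiner is: "The Dental Examiner(s) completing the dental examinations will be blinded to the subject sequence of treatments assigned". Nobody else is: "The subject, sponsor, and all other study staff will not be blinded to the treatment sequenced assigned".

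Inclusion criterion 3 in Section 4.2 limits entry to the sponsor's staff ("3M employee aged 18 years and older"). Exclusion criterion 7 removes members of the product team for the device.

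The toothpastes in Sections 5.1 and 5.5 are named retail products. A (no SLS) and C (high SLS) are other companies' brands. B (medium SLS) is the sponsor's: "subjects randomized to Treatment B will receive 1 tube of 3M ESPE Clinpro Tooth Creme toothpaste". Section 5.1 refers to the packaging for each composition, for example "The information on the components of Colgate toothpaste are listed on the packaging and safety data sheet". Section 5.4 sets out study labelling for the rinse bottles only. No section in the supplied text describes covering or coding the tubes.

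On recruitment, Section 4.4 states: "Potential subjects will be contacted once via e-mail to explain the purpose of the study". The study title names SLS, and Section 5.2 lists mild sloughing among the risks communicated to subjects.

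Section 9.4.1 defines the primary endpoint by either source: "All sloughing clinically observed or subject-reported over the three-week treatment period will be recorded as an adverse event". Acceptability is measured by the subject questionnaire (Section 6.4.3), and Section 9.4.2 says: "The data collected on the subject acceptance questionnaire will be summarized by treatment group". That section also plans an incidence based on the examiner's sloughing index, as a secondary outcome.

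**The concern.** The hypothesis in Section 9.1 is directional: more SLS, more sloughing. A subject who knows the product is high in SLS, and knows what the study is about, may look harder for sloughing, or record trivial changes, in that period. One such diary entry makes a primary event even if every blinded examination is clear.

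The model in Section 9.4.1 does not correct for this. The random subject effect absorbs a person's general tendency to report, and the period and sequence terms absorb time and order. Expectation attached to a toothpaste changes with the toothpaste within the same person, so it is estimated as part of the treatment effect.

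Acceptability is more exposed, because it has no blinded counterpart. Employees rating a regimen that includes their employer's toothpaste in one period and a competitor's in another may rate them differently for reasons unrelated to tolerability.

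Section 6.1 asks subjects not to discuss the study with one another in order to limit bias. The plan thus recognises bias on the subject's side, but leaves each subject's knowledge of their own toothpaste untouched.

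**Working it through.** **Route of the bias, by outcome**

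- Primary sloughing incidence (9.4.1): examiner-observed or subject-reported. The first route is blinded and the second is not, and either suffices.
- Index incidence (9.4.2): examiner only, so blinded, but secondary and limited to scheduled visits.
- Acceptability (6.4.3, 9.4.2): subject only, so unblinded.

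**The plan's own figure.** Section 9.2 gives 74% power for 72 versus 48 subjects at 50% versus 25%, using a two-sided Fisher's exact test at 0.05. Exact enumeration of two independent binomials gives 74.2% when the two-sided p is twice the smaller one-sided p, and 76.3% with the usual minimum-likelihood two-sided p. The first reproduces the plan. The second is used below.

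**Illustration.** The documents give no rate of expectation-driven reporting, so the following are assumptions.

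- True incidence: 25% on both B and C (25% is the Section 9.2 planning rate for n = 48).
- q: the share of sloughing-free C users who report sloughing because they know the paste.
- Apparent rate on C = 0.25 + 0.75 × q.

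| q on C | Apparent C | False C − B gap | Chance of a significant C vs B result |
|---|---|---|---|
| 0 | 25.0% | 0 | 3.8% |
| 5% | 28.75% | 3.8 points | 5.8% |
| 10% | 32.5% | 7.5 points | 12.1% |
| 15% | 36.25% | 11.3 points | 22.4% |

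The last column treats B and C as independent samples of 48 and 72. It is approximate, because the 48 subjects in sequences 2 and 3 contribute to both.

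The whole planning difference would be reproduced by q = 1/3, since 0.25 + 0.75/3 = 0.50.

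**If B users over-report too.** B also contains SLS. With 5% over-reporting on B, its apparent rate is 0.25 + 0.75 × 0.05 = 28.75%. With 10% on C, the gap is 32.5% − 28.75% = 3.75 points, and the chance of a significant result falls from 12.1% to 5.8%.

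**Loyalty to B.** Suppose 10% of true events on B go unreported: 0.25 × 0.90 = 22.5%. Against C this adds 2.5 points to the gap, in the direction of the hypothesis. If A also has a true 25%, B now appears 2.5 points below A, against the hypothesis.

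**Tubes to label** (Section 1.0 supply table): 24 + 48 + 72 + 72 washout = 216.

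**The case against.** The strongest reply is that this is a disclosed design choice with real safeguards. The examiner is blinded and examines at every visit, index-based incidence is already planned by treatment group, and product-team members are excluded. The rinse under investigation is used in every treatment period, so attitudes to the rinse are common to all toothpastes, and loyalty can differ only through B. All of that stands. It limits the concern for sloughing but does not remove it, because the blinded measure is not the primary endpoint, and it leaves acceptability unprotected.

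A reader might infer that the bias as a whole favours the hypothesis. The documents do not support that. SLS expectation points towards more reports on high SLS. Loyalty to B would help the B-to-C step and hurt the A-to-B step, and nothing in the documents shows that employees favour B.

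A reader might also infer that half of the primary events are exposed. Section 9.4.1 provides two qualifying routes, and no document says what share of events would be subject-report only.

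Nor can it be said that the recruitment letter tells subjects their SLS level or the expected direction. Appendix I is not in the supplied text.

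Two further replies have some force. Masking will be imperfect: sequences 2 and 3 meet all three products once the washout paste is counted, and taste or appearance may give them away. And knowing one's toothpaste resembles ordinary use, which may suit an acceptability question. However, the plan gives no such reason for leaving subjects unblinded.

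**Conclusion.** The concern holds as a route for bias. Unblinded subjects can generate primary events on their own report and supply all the acceptability data, and the planned model cannot separate expectation from a toothpaste effect. The blinded index incidence is a partial safeguard for sloughing only.

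The size is unknown. The 3.8 to 11.3 point false gap rests on an assumed true 25% on both B and C and an assumed 5% to 15% false reporting on C alone. It shrinks if B users over-report. For scale, Section 9.2 is built on a 25-point difference in a convenience sample meant to detect gross trends. These figures do not show that the primary result would be wrong, and such a conclusion should not be drawn from them. That the tubes are openly branded is inferred from the named products, the references to packaging and the absence of any masking step. The change is worth making because it is cheap, not because a large bias has been demonstrated.

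**What to change.** In Sections 5.5 and 8.2:

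- Have staff who neither dispense nor examine cover every treatment and washout tube with an opaque coded label. Use codes specific to the tube or subject, so that a shared letter does not reveal the product.
- Dispense by code, and do not tell subjects which SLS level they have. Check the recruitment letter and use instructions for consistency with this.
- Keep required use and ingredient information available to any subject who needs it for safety.
- Describe the result as partial subject masking (tube brand and SLS level concealed), and do not claim a double-blind design.

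Add one questionnaire item at Visits 3 and 6 asking the subject to guess the SLS level, and tabulate the guesses by toothpaste. Read them with care: a subject who has had sloughing may guess high SLS for that reason, so the item describes masking and should not be used for adjustment.

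The cost is labelling 216 tubes, one questionnaire item and small wording changes. Product, schedule and sample size do not change. The downside is that taste and appearance may leave masking incomplete.

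### Section 8.2 leaves whoever codes sloughing and whoever runs the analysis unmasked to toothpaste; the exposure is limited to the medium-SLS versus no-SLS contrast and is cheap to remove

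*Combined protocol and SAP*

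**What the plan says.** Section 8.2 sets the masking in two sentences. The first covers the examiner: "The Dental Examiner(s) completing the dental examinations will be blinded to the subject sequence of treatments assigned". The second covers everyone else: "The subject, sponsor, and all other study staff will not be blinded to the treatment sequenced assigned".

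Section 9.4.1 defines the outcome: "The primary endpoint is the incidence rate of sloughing". It then says how events enter it: "All sloughing clinically observed or subject-reported over the three-week treatment period will be recorded as an adverse event and coded using the MedDRA dictionary". A single MedDRA term, for exfoliation of the oral mucosa, is named in advance. The main analysis is a mixed logistic model. Fisher's exact test is a permitted, not mandatory, fallback: on all data if the model does not converge, or on Period 1 data if the treatment-by-period interaction is significant.

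At the end of Period 1 (6.3.3) the plan reads: "Dental Examiner will complete a dental examination, review subject diary, and record any AEs, as required". Sections 6.3.5 and 6.3.6 give the examiner the same diary review in Period 2.

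The documents do not say who does the MedDRA coding, what the coder can see, or which diary wordings count as sloughing. Under 8.1 the subject number identifies each case report form, and Appendix II prints the sequence for every subject number.

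**The concern.** A subject's own description of what happened in the mouth becomes a primary event when it is recorded and coded to the sloughing term. If the wording is vague, someone has to judge. A judge who knows the toothpaste may, without intending to, accept a borderline description more readily on high SLS than on no SLS. The hypothesis in 9.1 predicts exactly that gradient.

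The same applies to the analyst. Whether a model has failed to converge, and whether to use the fallback once it has, are judgements that 9.4.1 leaves open and that 8.2 allows to be made with assignments in view.

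Subjects and coordinators must know which toothpaste is dispensed. Coding and analysis come later and do not need that knowledge. At stake is whether a primary contrast involving the smallest group, 24 subjects on A, can be moved by a handful of unmasked decisions.

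**Working it through.** **Inputs.** Exposures from 8.1: A 24, B 48, C 72. Planning rates from 9.2: C 50% (36/72), B 25% (12/48), A 1% (about 0/24). Test from 9.2: two-sided Fisher, alpha 0.05. Groups are treated as independent, as 9.2 does.

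**The plan's own figures.** Section 9.2 states 74% power for C versus B and 77% for B versus A. Enumerating both binomials with a two-sided p equal to twice the one-sided Fisher p gives 74.2% and 77.6%, so the stated figures reproduce. The more usual two-sided Fisher p, which sums all tables no more probable than the one observed, gives 76.3% and 84.8%. Both versions are carried below as *doubled* and *usual*.

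**How far one event on A moves the bar on B (usual version).**

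- 0/24 against 8/48: the chance that all 8 events fall on B is C(48,8)/C(72,8) = 377,348,994/11,969,016,345 = 0.0315. The tables with 0, 1 or 2 events on B are less probable and add 0.0001 + 0.0014 + 0.0127. Total p = 0.046. With 7/48, p = 0.087.
- 1/24 against 12/48: tables with 12 or 13 of 13 events on B give 0.0236 + 0.0027. Tables with 5 or fewer on B add 0.0178 + 0.0036 + 0.0005. Total p = 0.048. With 11/48, p = 0.051.

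The bar on B moves from 8/48 = 16.7% to 12/48 = 25%. The doubled version also moves by four events, from 9/48 (p = 0.039) to 13/48 (p = 0.034). One event is 1/24 = 4.2 points on A but 1/72 = 1.4 points on C.

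**At the planned counts.**

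| Comparison | A = 0/24 | A = 1/24 |
|---|---|---|
| B 12/48 vs A, usual | 0.006 | 0.048 |
| B 12/48 vs A, doubled | 0.009 | 0.053 |
| C 36/72 vs A, usual | <0.00001 | 0.00002 |
| Three-group exact test | <0.00001 | 0.00002 |
| Cochran-Armitage trend | <0.00001 | 0.00001 |

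Trend with scores 0, 1, 2 and A = 1/24: total events are 1 + 12 + 36 = 49. T = (12 + 2×36) − (49/144)(48 + 2×72) = 84 − 65.33 = 18.67. V = (49/144)(95/144)(336 − 192²/144) = 0.2245 × 80 = 17.96. z = 18.67/√17.96 = 4.40. Even 6/24 on A leaves the trend at p = 0.006. C versus A stays significant up to 5/24 (doubled, p = 0.021) or 6/24 (usual, p = 0.036). C versus B does not involve A; one extra event on B moves it only from p = 0.008 (12/48) to 0.014 (13/48).

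**Averaged over the planning rates.** Among trials where B versus A is significant, one added event on A makes it non-significant in 44% (usual) or 54% (doubled). For C versus A the chance is about 0.03% (doubled).

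**Analysis route.** At a 1% rate, P(0/24 on A) = 0.99^24 = 79%. With no events on A the logistic model has no finite estimate for A, so the non-convergence branch is a realistic prospect. In the Period 1 branch (24 per group), B 6/24 against A 0/24 gives p = 0.022 and against 1/24 gives 0.097. C 12/24 stays significant up to A 4/24 (p = 0.031).

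**The case against.** A reader might infer that sponsor staff who know the toothpaste do the coding and in effect create the primary endpoint. The documents do not support that. No coder is named, and system and procedure details are redacted in 5.6 and 10.1, so a masked coding procedure may exist out of sight. A masked examiner observes the mouth, reviews the diary and records events before coding, and the target term is named in advance. Discretion is therefore confined to vague diary wording, and the documents give no estimate of how common that is. What remains is that 8.2 makes no exception for coder or analyst. A fixed target term does not settle which wordings map to it. Under 10.1 and 10.5, unmasked staff also review entries, check diaries and may scribe forms.

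A reader might also infer that one coding decision can change the trial's result. At planned rates it cannot change the trend, which is the main hypothesis, nor C versus A or the overall test. Even B versus A at exactly 12/48 stays significant with 1/24 in the usual Fisher version. Sensitivity to one event in 24 reflects group size and is not evidence of bias.

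On analyst discretion, the Fisher fallback has stated triggers, each tied to a data set, and 9.7 requires deviations to be justified. The looser wording in 9.4.2, "if appropriate, will be analyzed using a generalized linear regression model such as a Poisson model", governs secondary index outcomes only and says nothing about the primary test. What stands is narrower: the 9.4.1 fallback is optional once triggered.

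Finally, subjects' own open-label reports are a more direct route for bias, and masking the coder does not touch it. That is correct and limits what the change can achieve.

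**Conclusion.** The point holds in a limited form. As written, 8.2 permits coding of subject-reported sloughing and the choice of the primary fallback test to be made with the sequence known. The plan specifies neither masked coding nor a list of qualifying terms.

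The quantifiable exposure is in B versus A: one event on A raises the requirement on B from 8/48 to 12/48, and at the planning rates would overturn 44% to 54% of significant B versus A results, depending on the Fisher version. That contrast is one of only two for which 9.2 gives power, and 9.4.3 lists it among the pairwise adverse-event tests. The conclusion on the SLS trend is not at risk from one event at the planned rates.

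These figures assume independent groups, full follow-up and the rates in 9.2. The planned mixed model could behave somewhat differently. They show how much one event matters, not how likely a biased coding decision is. This merits an inexpensive amendment; it does not invalidate the design.

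**What to change.** - Amend 8.2 so that the MedDRA coder and the analyst, both named by role, are masked to sequence until database lock.
- Code verbatim terms from a listing stripped of subject number, period and toothpaste. Removing the toothpaste alone is not enough, because Appendix II links number and period to treatment. Dummy treatment labels would not mask the analyst either, since the exposure counts of 24, 48 and 72 identify the toothpastes.
- Before the sequence file is merged, fix the list of verbatim terms counted as sloughing. Also turn the 9.4.1 fallback into a rule: what counts as non-convergence, and that Fisher's test then will (or will not) be used.
- Read the masked-examiner incidence already planned in 9.4.2 (any non-zero index score) alongside the primary result. It needs no MedDRA coding and is the available check on bias from open-label reporting, which these changes do not remove.

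The cost is protocol wording and one stripped listing. The downside is that the randomization list, including the copy in Appendix II, must be withheld from two roles until lock. No visits or subjects are added.
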